5. SAMPLE SIZE JUSTIFICATION

No formal sample size calculation was conducted. The sample size of 8 per cohort (6 active: 2 Placebo) for the SAD and MAD cohorts is considered adequate for a Phase 1 FIH

study. The sample size of 10 subjects (all administered EIDD-2801) is in accordance with Food and Drug Administration (FDA) guidelines for sample size in food-effect studies.

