6. STUDY TREATMENTS

All treatments described are the planned treatments. The TFLs will reflect the actual treatments received, and dose levels will be displayed in increasing order where applicable. Screen failure subjects will have treatment ‘Screen Failure’ presented in all applicable listings.

6.1. Part 1

The study treatment names, abbreviations, and ordering to be used in the TFLs are presented in [Table 1](#).

Table 1: Presentation of Study Treatments in TFLs

Study Treatment	Order in TFLs
Placebo (fasted)	1
50 mg EIDD-2801 [REDACTED] (fasted)	2
100 mg EIDD-2801 [REDACTED] (fasted)	3
200 mg EIDD-2801 [REDACTED] (fasted)	4
400 mg EIDD-2801 [REDACTED] (fasted)	5
600 mg EIDD-2801 [REDACTED] (fasted)	6
800 mg EIDD-2801 [REDACTED] (fasted)	7
XXX mg EIDD-2801 [REDACTED] (fasted)	8

Additional treatment labels may be added in the same format if additional cohorts are required. Amend the formulation as required as changes may occur throughout the study. All Placebo groups will be pooled [REDACTED] for summaries but in the listings the formulation will be indicated in the treatment label as ‘Placebo [REDACTED] (fasted)’ or ‘Placebo [REDACTED] (fasted)’.

As the capsule formulation is expected to be utilized for the latter cohorts, the [REDACTED] EIDD-2801 treatment groups will be summarized after the [REDACTED] EIDD-2801 treatment groups.

6.2. Part 2

The study treatment names, abbreviations, and ordering to be used in the TFLs are presented in [Table 2](#).

Table 2: Presentation of Study Treatments in TFLs

Study Treatment	Order in TFLs
200 mg EIDD-2801 [REDACTED] (fasted)	1
200 mg EIDD-2801 [REDACTED] (fed)	2

Additional treatment labels may be added in the same format if additional cohorts are required. Amend the formulation as required as changes may occur throughout the study.

The study treatment sequence names, abbreviations, and ordering to be used in the TFLs are presented in [Table 3](#).

Table 3: Presentation of Study Treatment Sequences in TFLs

Study Treatment Sequence	Abbreviation	Order in TFLs
200 mg EIDD-2801 ██████ (fed) / 200 mg EIDD-2801 ██████ (fasted)	200 mg EIDD-2801 ██████ (fed/fast)	1
200 mg EIDD-2801 ██████ (fasted) / 200 mg EIDD-2801 ██████ (fed)	200 mg EIDD-2801 ██████ (fasted/fed)	2

Additional treatment sequences may be added in the same format if an additional cohort at a different dose level is required. Amend the formulation as required as changes may occur throughout the study.

6.3. Part 3

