8.5.3.1. Dose Proportionality

In Part 1 on day 1 a statistical analysis will be conducted to investigate the dose proportionality of the [REDACTED] formulation for PK parameters of EIDD-2801 and EIDD-1931 (AUC_{0-inf} , AUC_{last} , and C_{max}).

A statistical analysis will also be conducted to investigate the dose proportionality of the [REDACTED] formulation on day 1 for PK parameters of EIDD-2801 and EIDD-1931 (AUC_{0-inf} , AUC_{last} , and C_{max}) by combining the day 1 Part 3 data with the Part 1 [REDACTED] cohorts.

In Part 3 on day 6 a statistical analysis will be conducted to investigate the dose proportionality for PK parameters of EIDD-2801 and EIDD-1931 (AUC_{τ} , and C_{max}). The dose proportionality assessments will include dose levels from a common dietary state.

The PK parameters will be analyzed using a power model³ that will have the following form:

$$parameter = intercept \times dose^{slope} + random\ error$$

Using the natural log (ln) transformation,⁴ a power model can be expressed as a linear regression equation:

$$\ln(parameter) = intercept + slope \times \ln(dose) + random\ error$$

For dose proportionality, the slope of the regression line is equal to 1; for dose independence, it is equal to 0.

For each PK parameter separately, a pooled estimate (across all doses) of slope, corresponding 90% confidence interval (CI), and between-subject coefficient of variation (CV) will be calculated. Figures (on the logarithmic scale) containing individual values, power model line (90% CI), and dose proportionality line (defined as the power model line with slope of 1) will be created for each PK parameter; figures (on the semi-logarithmic scale) containing individual values and geometric means will be created for each corresponding PK parameter normalized by dose administered.

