The lack of fit test will be conducted for the statistical assessment of linearity assumption, and thus appropriateness of a power model. The lack of fit model will be the same as the power model fitted, but with dose included as additional fixed effect. The statistical assessment will rule the linearity assumption acceptable if the diagnostic plots appear reasonable and the lack of fit p-value >0.05 (dose effect is not significant at the 0.05 level of significance). The assessment of linearity assumption may also occur via visual examination of the figures by the pharmacokineticist. This assessment may override the statistical assessment; where this occurs, it will be detailed in the CSR.

It will be concluded that PK parameter is dose proportional for the dose range studied if the assumption of linearity is ruled acceptable and the 90% CI for the slope spans 1.

In the case of lack of dose proportionality, between treatment pairwise comparisons based on ln-transformed dose normalized PK parameters will be performed using an analysis of variance (ANOVA) model.⁵ The model will include dose as a factor. For each PK parameter separately, the least squares mean (LSM) for each dose, difference in LSMs between each

dose, and corresponding 90% CIs will be calculated; these values will then be back-transformed to give the GLSM, ratio of GLSMs, and corresponding 90% CI.

Examples of the SAS code that will be used are as follows:

Power Model Analysis

```
proc mixed data = <data in> alpha = 0.1;
  by parcat1n parcat1 pkday paramn param;
  model lpk = ldose / cl residual ddfm = kr2;
  ods output solutionf = <data out>;
run;
```

Power Model Analysis (Between-subject Variability)

```
proc mixed data = <data in> covtest alpha = 0.05;
  by parcat1n parcat1 pkday paramn param;
  class ldose;
  model lpk = ldose / cl residual ddfm = kr2;
  ods output covparms = <data out>;
run;
```

(Note: Pooled Geometric CV (%) = $100 * (\text{sqrt}(\text{exp}(\text{estimate}) - 1))$)

Power Model Analysis (Lack of Fit Test)

```
proc mixed data = <data in>;
  by parcat1n parcat1 pkday paramn param;
  class dose;
  model lpk = ldose dose / htype = 1 ddfm = kr2;
  ods output tests1 = <data out>;
run;
```

ANOVA Model Analysis

```
proc mixed data = <data in> alpha = 0.1;
  by parcat1n parcat1 pkday paramn param;
  class dose;
  model ldnpk = dose / cl residual ddfm = kr2;
  lsmeans dose / cl pdiff alpha=0.1;
  ods output lsmeans = <data out>;
  ods output diffs = <data out>;

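### The dose-proportionality rule turns a slope not shown to differ from 1 into a positive conclusion, so in small, narrow or noisy dose sets non-proportional kinetics can be declared proportional

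*SAP*

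**What the plan says.** SAP Section 8.5.3.1 fits a power model to each PK parameter by regressing ln(parameter) on ln(dose). The reference value is fixed: "For dose proportionality, the slope of the regression line is equal to 1; for dose independence, it is equal to 0". The slope is estimated with a 90% CI (the example code begins "proc mixed data = <data in> alpha = 0.1").

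Proportionality is then concluded "if the assumption of linearity is ruled acceptable and the 90% CI for the slope spans 1". The linearity assumption is accepted if diagnostic plots look reasonable and "the lack of fit p-value >0.05 (dose effect is not significant at the 0.05 level of significance"). The pharmacokineticist may also judge linearity by eye: "This assessment may override the statistical assessment; where this occurs, it will be detailed in the CSR".

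No margin, maximum CI width or inconclusive outcome is given. Pairwise comparisons of dose-normalised parameters are planned only where proportionality is lacking.

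On size, Section 5 says "No formal sample size calculation was conducted" and gives "The sample size of 8 per cohort (6 active: 2 Placebo) for the SAD and MAD cohorts".

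**The concern.** A 90% CI that contains 1 shows only that the data do not contradict proportionality. A wide interval contains 1 for many true slopes, and the rule does not limit the width. The lack-of-fit condition works the same way, since low power makes p > 0.05 more likely. Both conditions therefore favour the less informative data set.

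The SAP makes such data sets plausible. Each dose contributes six active subjects. The models are formulation-specific and restricted to a common dietary state (Section 8.5.3.1 and Appendix 1). Some groups have no calculable EIDD-2801 parameters (Section 10), so the EIDD-2801 models may lose dose levels.

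At stake are the report's wording on proportionality and the follow-up analysis. The dose-normalised comparisons would show the size of a departure, but they are not triggered after a pass.

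**Working it through.** The SAP states no power, CV or precision for this analysis, so there is no figure of its own to reproduce.

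**Inputs.** Six active subjects per dose (Section 5). Named doses of 50, 100, 200, 400, 600 and 800 mg in Part 1 (Table 1) and 50, 100, 200, 300 and 400 mg BID in Part 3 (Table 4). Two-sided 90% CI (Section 8.5.3.1). Between-subject CV of 30% and 50% is an assumption.

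**Formulas.**
- σ² = ln(1 + CV²): ln(1.09) = 0.0862, σ = 0.294 at CV 30%; ln(1.25) = 0.2231, σ = 0.472 at CV 50%.
- SE(slope) = σ/√Sxx, with Sxx the sum of squares of ln(dose) about its mean.
- Chance that the CI contains 1 = P(|T| ≤ t), with T noncentral t on n − 2 df, noncentrality (slope − 1)/SE, and t the 95th percentile of the central t.
- Departure over the range = r^(slope − 1), with r = highest dose/lowest dose.

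**Worked case: Part 3 Day 6, CV 50%, true slope 1.2.** n = 30, Sxx = 17.13, SE = 0.472/4.139 = 0.114, t = 1.701 on 28 df. The half-width is 1.701 × 0.114 = 0.194 and the noncentrality is 0.2/0.114 = 1.75. The chance that the CI contains 1 is 47%. The departure is 8^0.2 = 1.52-fold.

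**Results (CV 30% / CV 50%).**

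| Doses in model (mg) | n | Sxx | 90% CI half-width | True slope (departure) | CI contains 1 |
|---|---|---|---|---|---|
| Part 3 Day 6: 50–400, five doses | 30 | 17.13 | 0.121 / 0.194 | 1.2 (1.52-fold) | 13% / 47% |
| same | | | | 1.3 (1.87-fold) | 1% / 18% |
| Part 1: 50–800, six doses | 36 | 34.86 | 0.084 / 0.135 | 1.1 (1.32-fold) | 37% / 66% |
| same | | | | 1.25 (2.0-fold) | 0% / 8% |
| 50, 100, 200 only | 18 | 5.77 | 0.213 / 0.343 | 1.3 (1.52-fold) | 24% / 57% |

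The SAP does not show which doses share a formulation (redacted). The six-dose Part 1 row therefore assumes one formulation throughout, and the three-dose row is a hypothetical narrow set.

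**What a pass can hide.** In Part 3 at CV 50%, an estimated slope of exactly 1 with the half-width of 0.194 gives a dose-normalised ratio CI of 8^(−0.194) to 8^(0.194), or 0.67 to 1.50. The rule would call this proportional.

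**Effect of the linearity condition.** In 20,000 simulated trials under a power law, requiring lack-of-fit p > 0.05 as well lowered the 47% to 44% and the 57% to 55%. It tests curvature, not whether the slope is 1. A truly proportional parameter passes the CI condition 90% of the time and both conditions about 85%.

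**Effect of adding a margin (true slope 1, six doses 50–800 mg).** Slope limits are 1 ± ln(m)/ln(16).
- m = 1.25 (ratio 0.80–1.25): 0.2231/2.7726 = 0.080, limits 0.920–1.080; met in about 4% at CV 30% and 0% at CV 50%.
- m = 2 (ratio 0.5–2.0): 0.6931/2.7726 = 0.25, limits 0.75–1.25; met in about 100% and 84%.

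**The case against.** The strongest defence is that the reader is not misled. Slope, 90% CI, CV, fitted-against-proportional plots and dose-normalised plots are produced whatever the conclusion, and Section 8.1 urges caution because the sample size is not based on power. Proportionality is not listed among the objectives or endpoints in Sections 2 and 3. This stands as mitigation and lowers the severity. It does not alter the prescribed conclusion or restore the comparisons that a pass leaves out.

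Four stronger readings are tempting and are not supported:

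- *Clearly non-proportional kinetics pass in general.* They do not. Over 50–800 mg a two-fold departure passes in 0% or 8%. Linearity must also be accepted.
- *The later Part 1 cohorts might be modelled alone over 400–800 mg.* Section 8.5.3.1 combines that formulation's Part 1 cohorts with Part 3 Day 1 data, which widens the range. With seven doses over 50–800 mg and six subjects at each, a slope of 1.3 passes in 0% or 2%.
- *The visual override can declare a parameter proportional.* It reaches only the linearity assumption. The CI must still contain 1, the override can also act in the stricter direction, and its use must be described in the CSR.
- *The conclusion drives the dose for later trials.* Section 4.1 names a starting dose as the overall objective but does not tie it to this rule. Sections 4.1.1 and 9 base escalation on safety, tolerability and available PK data.

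A tight CI that narrowly misses 1 is less of a problem than it looks, because the pairwise ratios are then run and show how small the departure is.

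**Conclusion.** The rule is wrong as written and should be fixed; the severity is moderate. It draws a positive conclusion from two non-rejections, with no margin and no inconclusive outcome. With 6 active subjects per dose and an assumed CV of 30% or 50%, a 1.52-fold departure in Part 3 meets the CI condition in 13% or 47% of trials. If a model held only 50, 100 and 200 mg, the same departure would do so in 24% or 57%. Large departures over a wide range are mostly caught. The actual risk depends on the CV, which the SAP does not give, and on the formulation split, which is redacted. Estimates and intervals are unaffected; the conclusion and the conditional follow-up are.

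**What to change.** In Section 8.5.3.1:

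1. Replace the positive conclusion with a statement that a 90% CI containing 1 shows no evidence against proportionality over the range studied.
2. For every model, report r^(slope − 1), the ratio of dose-normalised geometric means at the highest versus the lowest dose. Obtain its 90% CI by putting the slope limits into the same expression.
3. Run the dose-normalised pairwise comparisons whatever the slope result.
4. Keep a conclusion of *dose proportional* only if the sponsor pre-specifies a margin for r^(slope − 1) and the 90% CI lies inside it. If the CI lies wholly outside the margin, the conclusion is *not proportional*; otherwise it is *inconclusive*.

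The margin is the sponsor's choice. The SAP gives none, and the figures above show that 0.80–1.25 would seldom be met at this sample size. If no margin is agreed, steps 1 to 3 correct the logic.

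The cost is a change of SAP wording, a few extra output lines per parameter, and fewer firm statements of proportionality. No new data are needed.

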8.5.3.2. Food-Effect

For Part 2 a statistical analysis will be conducted to investigate the food-effect by comparing treatments EIDD-2801 (fed) to EIDD-2801 (fasted) for PK parameters of EIDD-2801 and EIDD-1931 ($AUC_{0-\text{inf}}$, AUC_{last} , and C_{max}). If an additional cohort is enrolled with a different dose level then that cohort will be analyzed in a separate model.

The natural log (ln)-transformed PK parameters will be analyzed using a mixed model.⁶ The model will include planned treatment sequence, period, and actual treatment as fixed effects, and subject within planned treatment sequence as a random effect.

For each PK parameter separately, the least squares mean (LSM) for each treatment, difference in LSMs between the fed and fasted treatments, and corresponding 90% CIs will

be calculated; these values will then be back-transformed to give the GLSM, ratio of GLSMs, and corresponding 90% CI.

Additionally, the pooled estimate (across all treatments) of the within-subject coefficient of variation (CV) will be calculated, and residual plots will be produced to assess the adequacy of the model(s) fitted.

A statistical analysis using the Wilcoxon signed-rank test⁷ will be conducted to investigate the food-effect on the treatment by comparing the fed treatment to the fasted treatment for t_{max} . The median for each treatment, Hodges-Lehmann estimate of the median difference between the fed and fasted treatments, and corresponding 90% CIs will be calculated.

Examples of the SAS code that will be used are as follows:

Mixed Model Analysis

```
proc mixed data = <data in>;  
  by parcat1n parcat1 pckday paramn param;  
  class trtan aperiod trtseqp usubjid;  
  model lpk = trtan aperiod trtseqp / cl residual ddfm = kr2;  
  lsmeans trtan / cl pdiff = control('1') alpha = 0.1;  
  random intercept / subject = usubjid(trtseqp);  
  ods output lsmeans = <data out>;  
  ods output diffs = <data out>;  
  ods output covparms = <data out>;  
run;
```

Wilcoxon Signed-rank Test

```
proc univariate data = <data in> cipctldf(alpha = 0.1);  
  by parcat1n parcat1 pckday paramn param;  
  var ref test dif;  
  ods output quantiles = <data out>;  
  ods output testsforlocation = <data out>;  
run;
```

(Note: Derive Hodges-Lehmann estimates)

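### The power-model example code leaves the slope interval at the default 95% level, not the 90% level on which the SAP bases its dose-proportionality conclusion

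*SAP*

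**What the plan says.** SAP Section 8.5.3.1 promises, for each PK parameter, "a pooled estimate (across all doses) of slope, corresponding 90% confidence interval (CI") and a between-subject CV. It also plans a figure showing the power-model line with a 90% interval. The interval decides the conclusion: a parameter is called dose proportional if "the assumption of linearity is ruled acceptable and the 90% CI for the slope spans 1". If proportionality is not concluded, pairwise comparisons of dose-normalised parameters follow in an ANOVA.

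The SAS code is introduced with "Examples of the SAS code that will be used are as follows". The statements that matter are:

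- **Power model:** the procedure line is "proc mixed data = <data in> alpha = 0.1", the model line is "model lpk = ldose / cl residual ddfm = kr2", and the slope is collected with "ods output solutionf = <data out>".
- **Dose-normalised ANOVA:** alpha = 0.1 is on the procedure line and also on the line that makes the intervals, "lsmeans dose / cl pdiff alpha=0.1".
- **Food effect (Section 8.5.3.2):** the procedure line has no alpha. The level is set only where the intervals are made, "lsmeans trtan / cl pdiff = control('1') alpha = 0.1".

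**The concern.** In PROC MIXED, ALPHA= on the procedure statement sets the level of limits for covariance parameters. Limits for fixed effects requested by CL on the MODEL statement take their level from that statement's own ALPHA=, with default 0.05. The slope is a fixed effect, and the power-model MODEL statement carries no ALPHA=. Its limits are therefore 95% limits, although the text calls for 90%.

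The level matters because the decision is whether the interval includes 1. A wider interval includes 1 more often, whatever the true slope. The shift always favours a finding of proportionality, and such a finding also means that the follow-up ANOVA is not run. The rule applies to both analytes, to each listed parameter, and to all three planned power-model analyses: two on Day 1, by formulation, and one on Day 6 of Part 3.

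**Working it through.** **1. Level of the interval.** The SAP gives no sample size or power figure to reproduce (Section 5 states that no formal calculation was done). The figure to check is the confidence level.

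| Analysis | alpha on PROC line | alpha on the statement that makes the interval | Resulting level | Level in the text |
|---|---|---|---|---|
| Power model | 0.1 | none on MODEL (default 0.05) | 95% | 90% |
| Dose-normalised ANOVA | 0.1 | 0.1 on LSMEANS | 90% | 90% |
| Food effect | none | 0.1 on LSMEANS | 90% | 90% |

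Only the power model fails to match. With alpha = 0.1 on its MODEL statement, the level is 1 − 0.10 = 90%, as stated.

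**2. Width.** The half-width is t × SE(slope), with df = n − 2, so the ratio of widths is t(0.975, df) / t(0.95, df). Inputs are 6 active subjects per cohort (Section 5) and dose levels from Table 1 (Section 6.1) and Table 4 (Section 6.3). The dose sets are illustrations, because the formulation split is redacted and the number of subjects in each power model is not known.

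| Doses (mg) | n | df | t for 90% | t for 95% | Ratio |
|---|---|---|---|---|---|
| 50, 100, 200 | 18 | 16 | 1.746 | 2.120 | 1.214 |
| 50, 100, 200, 300, 400 | 30 | 28 | 1.701 | 2.048 | 1.204 |
| 50, 100, 200, 400, 600, 800 | 36 | 34 | 1.691 | 2.032 | 1.202 |

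**3. Effect on the decision.** SE(slope) = σ / √Sxx, where σ = √ln(1 + CV²) and Sxx is the sum of squares of ln(dose) about its mean. The probability that the interval includes 1 comes from the noncentral t with noncentrality (true slope − 1) / SE. The linearity condition is taken as met. The SAP gives no CV, so 30% and 50% are assumptions: σ = 0.2936 and 0.4724.

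Example: for 50, 100 and 200 mg, Sxx = 5.765. At CV 30%, SE = 0.2936 / √5.765 = 0.1223. For a true slope of 1.3 the noncentrality is 0.3 / 0.1223 = 2.45. The interval includes 1 with probability 0.241 at the 90% level and 0.365 at the 95% level.

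| Dose range (mg) | True slope | CV | Includes 1, 90% level | Includes 1, 95% level |
|---|---|---|---|---|
| 50–200 | 1.3 | 30% | 24.1% | 36.5% |
| 50–200 | 1.3 | 50% | 57% | 70% |
| 50–400 | 1.3 | 30% | 0.7% | 1.7% |
| 50–400 | 1.3 | 50% | 18% | 28% |
| 50–800 | 1.3 | 30% | about 0% | about 0% |
| 50–800 | 1.3 | 50% | 2% | 5% |
| 50–800 | 1.1 | 30% | 37% | 50% |

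If the true slope is exactly 1, the interval includes 1 in 95% of trials instead of 90%.

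**The case against.** **The text is right and the code is only an example.** This stands in part. The text says 90% throughout, so the planned method is sound and the defect is a mismatch between code and text. But the SAP says that this is the code that will be used, and Section 1 makes the approved SAP the template for the study report. A programmer who copies the line gets no warning about the level.

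**The line cannot be used as printed.** The code asks for the fixed-effects solution table but leaves out the SOLUTION option that creates it, so someone must edit the MODEL statement before any slope is reported. This is true. A reader might infer that the report will certainly carry 95% limits labelled as 90%, and the SAP does not support that: the final program is not shown, and the level may be corrected in the same edit. The risk remains, because adding SOLUTION does not add alpha.

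**The behaviour of the option is not stated in the SAP.** Correct, and SAS was not run for this check. The point rests on the syntax of the software that the SAP names. The ANOVA and food-effect code is consistent with it, since both set the level on the statement that makes the interval, but it is not proof: the double setting in the ANOVA could be harmless redundancy. One run settles the matter.

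**The plotted band.** A reader might infer that the 90% band in the figures is also wrong. No statement in the SAP produces that band, so its level cannot be judged from the code shown.

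**The effect is small in some designs.** This stands. At a true slope of 1.3 it almost disappears over 50 to 800 mg. It stays material for the narrow dose range and for slopes nearer 1.

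**Conclusion.** The concern holds as a mismatch between code and text. Used without an alpha on the MODEL statement, the example code gives a slope interval 20% to 21% wider than the one specified and tilts the decision towards proportionality. In the illustrations, the change in the probability of passing runs from nothing to about 13 percentage points (for example 57% to 70%, or 37% to 50%). These figures assume 6 active subjects with evaluable data at each dose, the dose sets shown, the stated CVs and an accepted linearity assumption.

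The reach is limited. PK in Parts 1 and 3 is a secondary objective (Section 2.2), and Section 8.1 already advises caution because the sample size is not based on power. The primary safety evaluation is untouched. The food-effect and ANOVA intervals carry their own level and are correct; what is affected is whether the ANOVA is triggered.

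**What to change.** Change the power-model statement to `model lpk = ldose / solution cl alpha=0.1 residual ddfm=kr2;`. SOLUTION is needed for the requested table, and alpha=0.1 gives the 90% limits. Before the limits are used, confirm that the Alpha column of the output dataset reads 0.1. Make sure that the program for the plotted power-model band, which the SAP does not show, uses the same level. The 90% in the text stays as it is. The cost is one line in the SAP and in the analysis program, plus one check of the output.
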